6.1.4. Handling of Dropouts or Missing Data

[figure not shown]
The original plan was that every attempt would be made to ensure participants remain in the study to completion and all data is collected as scheduled, the occurrence of missing data cannot be completely prevented. The early study termination creates more missing data than originally anticipated. However, the administrative censoring is independent of the treatments and outcomes in this study and is therefore considered missing completely at random. Therefore, the missing data from early stopping will not bias the MMRM results.

An incomplete start or stop date of an AE or a medication will be imputed as described in section 6.1.8.

Any participant who withdraws from the study will be considered to have missing data at all subsequent visits. The primary analytic approach for efficacy assumes missing at random (MAR) to estimate what would have been observed if the participant had not discontinued. A reference-based multiple imputation sensitivity analysis (copy reference) will be employed in which missing not at random is assumed such that after discontinuation, drug-treated participants will have placebo-like values imputed for their missing data.

If up to two individual items of the total 12 items for the ADAS-Cog12 (maximum score = 80) are missing for non-cognitive reasons, the total score will be imputed by multiplying the observed score (i.e. the score for the non-missing items) by a factor that includes the maximum scores for the missing item(s) as follows:

Version 1.0 | 28-Feb-2025 Page 20 of 56

Imputed score = Observed score * (80/[80-maximum score for missing items]).

As an example, if the first item "Word Recall" (maximum score = 10) and the second item "Commands" (maximum score = 5) are missing, the observed score will be multiplied by the factor 80/(80-[10+5]) or 80/65 or 1.23. The imputed score will be rounded to the nearest integer. ADASCog12 tests with more than two missing items will be considered missing scores.

Missing items on other assessments will not be imputed; such scores will be considered missing.

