- 9. Male subjects must be willing to use contraception during the study. With female partners of childbearing potential, male subjects, regardless of their fertility status, must agree to either remain abstinent or use condoms in combination with one additional highly effective method of contraception (e.g., oral or implanted contraceptives, or intrauterine devices) or an effective method of contraception (e.g., diaphragms with spermicide or cervical sponges) during the study and for 14 days after Study Drug dosing has been completed.
- 10. Fluency in a language of the research site and the utilized assessment materials.
- 11. Has adequate visual and auditory acuity (in the Investigator's judgment) that is sufficient to complete all scheduled assessments (eyeglasses and hearing aids are permitted).
- 12. If receiving background AD medications, including cholinesterase inhibitors, memantine, neuroleptics, anxiolytics, or sleep medications, the dosing regimen must be stable for at least 12 weeks prior to Study Day 1 (randomization) and should be expected to remain stable during the study (Note barbiturates, meprobamate, and high dose benzodiazepines are not allowed, while low dose benzodiazepines, zolpidem, zaleplon and suvorexant are permitted). Chronic medications for conditions other than AD (such as depression) must be prescribed at a stable dose for at least 4 weeks prior to screening. Medications that might have a potential confounding effect on cognitive testing (either prescription or non-prescription medications) should not be modified during the Screening Period (see Section 6.3 for additional details).
- 13. The subject has not been a cigarette smoker or chewed tobacco for at least 3 years (occasional pipe or cigar smoking is permitted, but vaping is not).
- 14. Availability of a person (a study partner) who has frequent and sufficient contact with the study subject (defined as ≥10 hours per week), and can:
  - a. provide accurate information regarding the study subject's cognitive and functional abilities in the opinion of the Investigator,
  - b. agree to comply with and participate at all scheduled visits and study procedures,
  - c. sign the necessary consent form,
  - d. maintain the same level of interaction with the study subject throughout the study duration.
- 15. Individuals who have participated in a clinical study with an investigational drug

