# 8.5. ALZHEIMER'S DISEASE COOPERATIVE STUDY – ACTIVITIES OF DAILY LIVING (ADCS-ADL-AD)

The ADCS-ADL is a 23-item study partner questionnaire that covers both basic activities of daily living (ADL) (e.g., eating and toileting) and more complex ADL or instrumental ADL (e.g., using the telephone, managing finances, preparing a meal).

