6.1.7. Derived Variables and Conventions

Age: the age at baseline will be used.

Alzheimer's disease status

- MMSE = 21-27 (mild dementia)
- MMSE = 16-20 (moderate dementia)

Change from baseline = post-baseline value at timepoint – value at baseline

Time since diagnosis of AD (months) = (date of first dose – date of diagnosis) / 30.4375

Treatment duration (days) = (date of last dose of study drug – date of first dose of study drug) +1

Study Drug Exposure = treatment duration (days), that is the number of days a participant is on study drug will be calculated as the number of days from date of first dose to date of last dose plus 1.

Study Drug Compliance (%) = 100 x Total number of tablets taken / Total number of expected tablets. That is, study medication compliance will be calculated based on the numbers of tablets dispensed minus the number of tablets returned divided by the expected number of tablets based on the duration of the participant's participation in the study.

Study drug compliance will not be calculated for participants whose date of last study drug is unknown.

Total Dose (mg) = \sum [Number of doses taken_i x Dose received (mg)_i] where,

[figure not shown]
i = 1 to k, (k = number of time periods participant is receiving a constant dose)

Average Daily Dose (mg/day) = Total Dose (mg) / Treatment Duration (days)

Dose variables (dose, total dose, and average daily dose) not calculated for placebo participants.

The iADRS for this trial is a composite endpoint that combines scores from the 12-item AD Assessment Scale-Cognitive subscale (ADAS-Cog12) and the AD Cooperative Study - instrumental Activities of Daily Living (ADCS-iADL). The ADCS-iADL is defined as items 6a and 7-23 of the ADCS-ADL.

Version 1.0 | 28-Feb-2025 Page 22 of 56

iADRS score = [-1(ADAS-Cog12) + 80] + ADCS-iADL

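### SAP 6.1.4 voids the co-primary ADCS-ADL total for any one missing item of 23 but prorates ADAS-Cog12 for up to two of 12; if eCOA lets items be skipped, near-complete function assessments are discarded

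*SAP*

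**What the plan says.** SAP 6.1.4 sets two item-level rules.

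- **ADAS-Cog12.** The proration rule opens: "If up to two individual items of the total 12 items for the ADAS-Cog12 (maximum score = 80) are missing for non-cognitive reasons". The observed score is then multiplied by 80 over 80 less the maximum of the missing items, and rounded to an integer. Beyond two, "ADASCog12 tests with more than two missing items will be considered missing scores".
- **All other scales.** "Missing items on other assessments will not be imputed; such scores will be considered missing".

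Protocol 8.5 describes the ADCS-ADL as a "23-item study partner questionnaire that covers both basic activities of daily living" together with more complex, instrumental ones. SAP 6.1.7, 8.1, 8.1.1 and 8.2 contain no separate ADCS-ADL item rule, so the second rule governs it.

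The iADRS (SAP 6.1.7) is 80 minus ADAS-Cog12, plus the ADCS-iADL, and "The ADCS-iADL is defined as items 6a and 7-23 of the ADCS-ADL". That is 1 + 17 = 18 items. SAP 6.1.3 tests the iADRS first among the secondary endpoints. Protocol 11.3.1 makes success depend on both co-primaries.

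The primary model (SAP 8.1) analyses change from baseline with the baseline score as a covariate. In the Schedule of Activities the ADCS-ADL is collected at the Baseline Visit but not at screening. Protocol 8.9 puts both co-primary scales on the same eCOA platform and does not say whether an item can be left unanswered.

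**The concern.** The two co-primaries are treated unequally and no reason is given. Up to 2/12 = 16.7% of ADAS-Cog12 items may be absent for non-cognitive reasons and the score survives. On the ADCS-ADL, 1/23 = 4.3% of items absent is enough to lose it. The other 22 answers are thrown away, and often the iADRS with them.

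The respondent is a study partner who "has frequent and sufficient contact with the study subject (defined as ≥10 hours per week", so an isolated item that cannot be answered is conceivable.

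The consequence depends on the visit. After baseline, a voided total is one missing visit, and the MMRM still uses the participant's other visits. At baseline, both the change score and the covariate are undefined, the schedule offers no earlier ADCS-ADL to fall back on, and the participant leaves the ADCS-ADL model. The SAP's argument that the extra missing data are completely at random covers only the administrative stop, not item gaps, which could depend on the partner or on severity. Voiding forms therefore adds reliance on the missing-at-random assumption for an endpoint the trial cannot succeed without.

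**Working it through.** **1. The plan's own figures.** SAP 2.2 assumes a placebo change of 6.0, a 45% difference (0.45 × 6.0 = 2.7 points), SD 10.0, two-sided 0.05 and 90% power, all for ADAS-Cog. Then n = 2 × [10 × (1.960 + 1.282)/2.7]² = 288.3, so 289 per group, with power 90.1%. Allowing for 20% dropout, 289/0.80 = 361.25, against 361 stated. The SAP's proration example, 80/65 = 1.23, also reproduces. None of these is in error.

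**2. Inputs for the item rules.** There are 23 ADCS-ADL items (Protocol 8.5), 18 instrumental items (SAP 6.1.7) and 12 ADAS-Cog12 items (SAP 6.1.4). The per-item missing probability q is *not in the documents*. It is assumed equal and independent across items, at 0.1%, 0.5% and 1%.

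**3. Share of scores voided at one visit.**

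- ADCS-ADL, current rule: 1 − (1 − q)^23
- ADCS-iADL, current rule: 1 − (1 − q)^18
- ADAS-Cog12: P(3 or more of 12 missing), taking all gaps as non-cognitive
- ADCS-ADL with a two-item tolerance: P(3 or more of 23 missing)
- ADCS-ADL change score, needing two complete forms: 1 − (1 − q)^46

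| q | ADCS-ADL | ADCS-iADL | ADAS-Cog12 | ADCS-ADL, two-item tolerance | ADCS-ADL change score |
|---|---|---|---|---|---|
| 0.1% | 2.3% | 1.8% | <0.001% | 0.0002% | 4.5% |
| 0.5% | 10.9% | 8.6% | 0.003% | 0.02% | 20.6% |
| 1% | 20.6% | 16.5% | 0.02% | 0.15% | 37.0% |

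The last column assumes the same q at baseline and at follow-up. For a given q, independence is the unfavourable case: gaps clustered in the same forms void fewer forms.

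**4. What a Week 76 void could cost.** No effect size or SD is given for ADCS-ADL, so the ADAS-Cog standardised effect (2.7/10 = 0.27) is borrowed, with 289 per arm.

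- *No recovery:* n = 289 × (1 − share voided) gives 282, 258 and 229 per arm, and power of 89.4%, 86.5% and 82.4%.
- *Partial recovery from an earlier visit:* with an assumed Week 64 to Week 76 correlation ρ and share voided v, effective n = 289/[(1 − ρ²)/(1 − v) + ρ²]. At q = 1%, ρ = 0.70 gives 255 and 86.2%; ρ = 0.85 gives 270 and 88.0%.
- *Two-item tolerance:* power is 90.0% to 90.1% at all three rates.

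These figures concern post-baseline voids only; a voided baseline is not recovered. They use the planned group size, not the mITT set or the numbers left after early termination, so they show scale and do not estimate this trial's power.

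**5. Scale maxima for a parallel rule.** The ADCS-ADL maximum is 78 (SAP 3.2). The ADCS-iADL maximum is 139 − 80 = 59, from the iADRS range (SAP 3.1.2) and the ADAS-Cog12 maximum.

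**The case against.** The strongest reply is that no loss has been shown. The scales are captured electronically by qualified raters, the eCOA vendor reviews quality and the CRO can query sites (SAP 4.1). If the platform forces every item, the rule never bites. **This stands as to size:** the loss may be near zero. It does not remove the inconsistency, because ADAS-Cog12 is captured on the same platform and the SAP still provides for its missing items.

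The evidence for unanswerable items is thin. Ten hours a week is a minimum, and inclusion criterion 14 also requires a partner who, in the Investigator's opinion, can inform accurately on function and will keep up the same level of contact. The documents do not give the ADCS-ADL response options, so an answer of not knowing might be scored and not left blank. **Both points stand**; they make gaps less likely but do not exclude them.

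Proration has its own bias. It assumes the missing activity is performed at the participant's average level on the others. If instrumental items are more impaired than basic ones, prorating a missing instrumental item overstates function. **This stands** as the price of the change. The SAP accepts the same kind of assumption for ADAS-Cog12, but only for non-cognitive reasons, so an extension needs a matching condition.

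A reader might infer that a fifth of the function data is being lost, or that power falls to 82%. The documents do not support this. Those figures rest on an assumed 1% rate, independence across items, a borrowed effect size and, for power, no recovery by the MMRM.

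**Conclusion.** The point holds in conditional form. The rule is explicit and unequal. If eCOA permits skipped items, it discards near-complete assessments of a required co-primary, and of the first-ranked secondary endpoint when the gap is among the 18 instrumental items. After baseline the cost is precision, partly recovered; at baseline it is the participant's whole contribution to the ADCS-ADL model. The size runs from near zero under forced completion to 2.3%, 10.9% or 20.6% of totals per visit at the assumed rates, which is an upper range. The SAP already holds a workable formula and its extension is cheap, so the change is worth making even though the rate is unknown. The planned sample size is not in question.

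**What to change.** Amend SAP 6.1.4 before unblinding:

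1. When up to two of the 23 ADCS-ADL items are missing for reasons unrelated to the participant's condition, set the total to observed × 78/(78 − maximum of the missing items), rounded as for ADAS-Cog12.
2. Do the same for the ADCS-iADL with its maximum of 59, so that the iADRS follows.
3. Treat the score as missing when more than two items are missing.
4. Report the number of prorated and voided totals by arm and visit, and keep the complete-items-only rule as a sensitivity analysis.
5. State whether eCOA allows an item to be skipped.

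The cost is a few SAP sentences, one derivation and one table. The individual item maxima must come from the scoring manual, as they are not in the protocol or SAP. The statistical cost is the average-level assumption, which the sensitivity analysis exposes. If eCOA forces completion, the new rule is never triggered and changes nothing.

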6.1.5. Analysis Visit Windows

All scheduled visits and associated variables for the treatment phase will be analyzed based on the study week to which they are assigned.

For the safety summaries and analyses, scheduled analysis visits will be windowed to the nearest scheduled visit and the unscheduled visits/assessments and early termination visits will be mapped to a scheduled visit using the following visit windows (Table 2.1 and Table 2.2). Visit windows will be assigned by splitting the periods between visits at the mid-point between the visits.

If both scheduled and unscheduled visits fall within the same visit window, scheduled visit will be used over unscheduled visits. If both scheduled and early termination visits fall within the same visit window, the data from the early termination visit will supersede.

If more than one unscheduled visit falls within the same visit window, the one closest to the target date will be used in the analysis. If equidistant, the earliest visit will be used.

If the analysis visit (for Unscheduled or ET assessments) falls on a visit window in which that specific assessment is not scheduled, then that assessment will not be used for analysis.

Table 2.1: Visit Windows for Safety (Except for ECG) Analysis

Scheduled Visit	Scheduled Visit Day	Window for Assignment of
	(Target Day)	Analysis Visit (Study Days ¹)
Week 4	Day 29	Day 2 – Day 71
Week 16	Day 113	Day 72 – Day 155
Week 28	Day 197	Day 156 – Day 239
Week 40	Day 281	Day 240 – Day 323
Week 52	Day 365	Day 324 – Day 407
Week 64	Day 449	Day 408 – Day 491
Week 76	Day 533	Day 492 – Day 575

¹Study Day relative to the date of first dose of study drug.

Table 2.2: Visit Windows for Safety (ECG only) Analysis

Scheduled Visit	Scheduled Visit Day	Window for Assignment of
	(Target Day)	Analysis Visit (Study Days ¹)
Week 4	Day 29	Day 2 – Day 155
Week 40	Day 281	Day 156 – Day 407
Week 76	Day 533	Day 408 – Day 659

¹Study Day relative to the date of first dose of study drug.

For the efficacy summaries and analyses, scheduled analysis visits are visits upon scheduled time points as specified in the Schedule of Time and Events. Scheduled analysis visits will be windowed

Version 1.0 | 28-Feb-2025 Page 21 of 56

to the nearest scheduled visit. Assessments that fall within the same window will be averaged. There will be one valid value of assessment kept for each scheduled analysis visit in summary / analysis statistics.

Unscheduled visits are visits with data not collected at scheduled time points. Unscheduled visits will be windowed to the nearest scheduled visit as described above. All unscheduled visits will be included as collected in eCRF in listings.

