#### 7.1. EVALUATIONS BY VISIT

Follow-up visits can be scheduled  $\pm$  five (5) days from the targeted Study Visit date.

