#### 9. EARLY DISCONTINUATION

Subjects may choose to discontinue Study Drug or study participation at any time, for any reason, and without prejudice. Moreover, a subject may be withdrawn at any time at the discretion of the Investigator or Sponsor for safety, behavioral or administrative reasons. Discontinued subjects should be followed according to medical practice standards, and the outcome documented. Follow-up is required if the subject is discontinued due to an adverse event (AE). Any comments (spontaneous or elicited) or complaints made by the subject and the reason for termination and the date of stopping the drug must be recorded in the Case Report Form (CRF) and source documents.

The following must be completed and documented in the source documents and CRFs for all subjects who discontinue the study early:

- The reason for early study discontinuation. If the subject is withdrawn for more than one reason, each reason should be documented in the source documents and the most clinically relevant reason should be entered on the CRF.
- Vital signs (blood pressure, temperature and pulse), brief physical and neurologic examination, weight, clinical laboratory tests, 12-lead resting ECG (5 min supine), use of concomitant medications and adverse events should be obtained at discharge prior to release.
- Blood draw for plasma biomarkers
- ADAS-Cog12, MMSE, CDR, ADCS-ADL, NPI, ZBI and C-SSRS (as detailed in Section 7.1.7 Early Termination Visit), if not performed within the last 30 days.

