3.2.1. Safety Endpoints

The safety endpoints of this study include the following:

• Incidence of adverse events (AEs) including treatment-emergent, serious, related to study

Version 1.0 | 28-Feb-2025 Page 16 of 56

drug, and leading to withdrawal along with AEs by severity and relationship to study drug

- Mean change in clinical laboratory values from baseline to Weeks 4, 16, 28, 40, 52, 64 and 76. Shifts in the normality of clinical laboratory values from baseline to Weeks 4, 16, 28, 40, 52, 64 and 76.
- Mean change in vital signs (blood pressure [supine], temperature, pulse rate) from baseline to Weeks 4, 16, 28, 40, 52, 64 and 76.
- Mean change in body weight from baseline to Weeks 4, 16, 28, 40, 52, 64 and 76.
- Shifts in physical exam (PE) findings from baseline to Weeks 4, 16, 28, 40, 52, 64 and 76.
- Shifts in neurological exam (NE) findings from baseline to Weeks 4, 16, 28, 40, 52, 64 and 76.
- Mean change in ECG parameters from baseline to Weeks 4, 40 and 76.
- Concomitant medications/treatments usage
- Shifts in the C-SSRS from baseline to Weeks 4, 16, 28, 40, 52, 64 and 76.

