All statistical comparisons will be based on LS means from the relevant contrasts in the mixed model for repeated measurements (MMRM) or analysis of covariance (ANCOVA).

The data from nominal/scheduled protocol clinic visits will be included in visit-based summary tables. Unscheduled assessments, if they occur, and the ET visit data will be mapped to scheduled assessments according to the visit windows defined in section 6.1.5 for all safety and efficacy analyses. See Section 6.1.4 and 6.1.5 of this SAP for more details.

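### SAP 6.1.5 lets an early-termination ECG replace a correctly timed Week 4 or Week 40 ECG in the by-visit tables with a reading up to 126 days later

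*SAP*

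**What the plan says.** SAP 4.2 states that "the ET visit data will be mapped to scheduled assessments according to the visit windows defined in section" 6.1.5, for safety and efficacy alike. For safety data, SAP 6.1.5 sets the windows at the mid-points between scheduled visits. Table 2.2 gives the ECG windows: Days 2 to 155 for Week 4, "Day 156 – Day 407" for Week 40, and "Day 408 – Day 659" for Week 76.

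The same section then gives precedence rules. A scheduled reading beats an unscheduled one, and two unscheduled readings are settled by closeness to the target date. For ET visits the rule runs the other way: "If both scheduled and early termination visits fall within the same visit window, the data from the early termination visit will supersede". A further rule says that an unscheduled or ET assessment that "falls on a visit window in which that specific assessment is not scheduled, then that assessment will not be used for analysis".

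Protocol section 9 requires, for everyone who stops early, "12-lead resting ECG (5 min supine), use of concomitant medications and adverse events should be obtained at discharge prior to release". The 30-day exemption in Protocol 7.1.7 and section 9 covers only the clinical rating scales. SAP 3.2.1 names the safety endpoint: "Mean change in ECG parameters from baseline to Weeks 4, 40 and 76".

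**The concern.** The by-visit ECG tables are meant to show the change from baseline at about 4, 40 and 76 weeks of treatment. When a discontinuer has both an on-time ECG and a later ET ECG in one window, the SAP puts the later one in the visit row and leaves the on-time one only in the listings. The row then carries a reading from a different time point, although a correctly timed one was taken.

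The rule ignores distance from target, so its effect grows with window width. ECG windows are the widest in the plan because there are only three post-baseline ECG visits. What is at stake is how faithfully a named safety endpoint is described for people who stopped early.

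**Working it through.** **Inputs.** Target days (29, 281, 533) and window limits come from SAP Tables 2.1 and 2.2. The visit tolerance is plus or minus "five (5) days from the targeted Study Visit date" (Protocol 7.1). The ECG schedule is in Protocol 7.1.4 to 7.1.7, and the discontinuation ECG in Protocol section 9.

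**1. Reproduce the plan's windows.** Target day = 7 × week + 1, which gives 29, 281 and 533. The mid-points are (29 + 281)/2 = 155 and (281 + 533)/2 = 407. The last limit is 533 + (533 − 281)/2 = 659. All agree with Table 2.2.

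**2. Can a scheduled and an ET ECG share a window?** Yes. ECGs are scheduled at Weeks 4 and 40, an ECG is required at discontinuation, and a recent scheduled ECG does not waive it. At Week 76 the scheduled visit is itself the end of treatment, so no later ET visit is expected there.

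**3. Does the exclusion rule remove the ET ECG?** No. Table 2.2 runs without a gap from Day 2 to Day 659, and every window belongs to a visit with a scheduled ECG.

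**4. Largest displacement, scheduled ECG on the target day.** Displacement = day of ET ECG − day of scheduled ECG.
- Week 4: 155 − 29 = 126 days. Day 155 is (155 − 1)/7 = Week 22.
- Week 40: 407 − 281 = 126 days. Day 407 is (407 − 1)/7 = Week 58.
- 126/7 = 18 weeks in each case.

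**5. With the visit tolerance.**
- Scheduled visit 5 days early: 155 − 24 = 407 − 276 = 131 days.
- Scheduled visit 5 days late: 155 − 34 = 407 − 286 = 121 days.

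**6. Smallest displacement.** An ET ECG on Day 30 or Day 282 moves the value by one day. ET ECGs on Days 30 to 34 or 282 to 286 are themselves within 5 days of target, so substitution there is harmless.

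**7. Comparison with other safety data.** The same rule under Table 2.1 displaces a value by at most 71 − 29 = 42 days at Week 4. It is also 42 days at each later visit through Week 64 (for example 491 − 449). The ECG limit is 126/42 = 3 times as large.

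**The case against.** The strongest reply is that this is a stated choice. The opposite treatments of unscheduled and ET readings stand in adjacent sentences, which looks deliberate, and Table 2.2 tells the reader which days each row covers. The last on-study ECG reflects the longest exposure, and simply reversing the precedence would drop it from the tables whenever it shares a window. This has force: no other text is breached, and the discontinuation ECG should stay visible. A separate row meets that need without discarding the on-time value.

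A second reply is that SAP 9.4 names the last ECG visit Week 76/ET/ED, and the same combined label appears for laboratory tests, vital signs, examinations, MRI and C-SSRS, and in the protocol's Schedule of Activities. If ET ECGs went to that row, nothing at Weeks 4 or 40 would be overwritten. But SAP 4.2 and 6.1.5 state the window mapping explicitly, and 6.1.5 is the more specific text. The label leaves some doubt without removing the point.

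A third reply is that the consequence is small. That stands. SAP section 9 makes the safety summaries descriptive, SAP 9.4 keeps every ECG in the listings, and Protocol 10.1 makes new clinically significant abnormalities in physiological testing adverse events. Efficacy is untouched, because efficacy assessments sharing a window are averaged.

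A reader might go further and infer that the mid-point windows themselves are wrong. They are not. A Day 156 ECG is 125 days from Week 40 and 127 from Week 4, so it goes to the nearest ECG visit, as the SAP says it will. Where an ET ECG is the only one in its window, no better-timed reading is displaced.

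**Conclusion.** The point holds and is minor. In the descriptive by-visit ECG tables, a discontinuer's target-day Week 4 or Week 40 reading can be replaced by one up to 126 days later, or 131 days if the scheduled visit was 5 days early. These are extremes that need termination on the last day of the window.

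The conclusion assumes that the mapping in SAP 4.2 and 6.1.5 governs over the label in 9.4, and that the ECG required at discontinuation is actually taken.

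Two stronger readings are not supported. One is that QT/QTc outliers are lost: SAP 9.4 does not say whether the category tables (14.3.8.3 and 14.3.8.4) use windowed values, so this needs clarifying and has not been shown. The other is that the ECG safety findings are biased, perhaps widely, because the study was stopped early. The documents give neither the number of participants with two ECGs in one window nor any basis for a direction.

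**What to change.** In SAP 6.1.5, state that when a scheduled and an ET assessment fall in the same window, the scheduled value is used for that visit row and the ET value is reported in a separate ET/last on-study row. Apply this to Table 2.1 as well as Table 2.2, so that all safety domains follow one rule. Leave the mid-point windows as they are for an ET ECG with no scheduled ECG in its window.

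Optionally, state in SAP 9.4 that the QT/QTc category tables also show each participant's worst post-baseline value over all scheduled, unscheduled and ET ECGs. Windowing could then not remove an extreme value.

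The cost is a few sentences and one extra row per table, with no new data. The extra row mixes exposure durations and should be footnoted accordingly. If the tables have already been produced, a supplementary ECG table on this basis would serve.
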